5.15.1.8. Use of other Blood Products and Hemostatic Agents

Use of blood product and hemostatic agents after the start of and exanet treatment will be provided as a data listing by patient.

5.15.1.9. Re-Bleeding

Re-bleeding data will be listed with FXa inhibitor, initial bleeding type, and and exanet dose.

5.15.1.10. Change in Clinical Neurologic Status for ICH Patient Population

Clinical neurologic status evaluation will be based on mRS, GCS, and the NIHSS scores. The primary goal of these scale analyses is to detect any clinical worsening in ICH patients. For the mRS, the number of patients with score of zero to 2, inclusive (i.e., qualified as success) and of patients with score greater than 2 as failure. The proportion of events and the 95% Fisher exact confidence interval will be presented for baseline, 1 hour after the end of the andexanet infusion, 12 hours after the end of the andexanet infusion, and at Day 30 follow-up. Exact 95% CI will be presented.

The GCS will be evaluated at baseline, at 1 hour after the end of the andexanet infusion, 12 hours after the end of the andexanet infusion, and at Day 30 follow-up. Each patient will be rated for all three domains (i.e., Eye Opening, Verbal Response, and Best Motor Response). The sum of the three domains score will be summarized as the raw value and change from baseline. Analysis will be performed including patients in the efficacy population with ICH bleeding. Mean, standard deviation, median, 95% CI for the median will be presented.

The NIHSS scores will be performed at baseline, at 1 hour after the end of the andexanet infusion, 12 hours after the end of the andexanet infusion and at Day 30 follow-up. The NIHSS is composed of 11 items, each of which scores a specific ability between a 0 and 4. The individual scores from each item are summed in order to calculate a patient's total NIHSS score. The patient total score will be analyzed as raw scores and as change from baseline. Analysis will include all patients in the efficacy population with ICH bleeding. Mean, standard deviation, median, 95% CI for the median will be presented.

Analyses will be presented for the overall population and by FXa inhibitor.

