3.0 INVESTIGATIONAL PLAN

3.1. Overall Study Design and Plan: Description

This is a multicenter, prospective, open-label study of and exanet in patients presenting with acute major bleeding who have recently received one of the following FXa inhibitors: apixaban, rivaroxaban, edoxaban, or enoxaparin. Attempts will be made to enroll patients on direct FXa inhibitors as well as those on indirect FXa inhibitors, and to limit the percentage of enrolled patients receiving indirect FXa inhibitors to $\leq 20\%$. A minimum of approximately 110 evaluable patients with ICH, 50 of whom are considered to be high-risk as determined by the core lab, will be enrolled in the study. In order to achieve sufficient numbers of ICH patients, enrollment in other subgroups (e.g., patients with non-ICH bleeds) may be capped by the Sponsor.

Once consent is obtained and eligibility criteria are confirmed, patients with acute major bleeding will receive and exanet as an IV bolus administered over ~15 to 30 minutes, followed immediately by a continuous infusion administered over ~120 minutes. The start of the and exanet bolus must be within 18 hours following the last dose of FXa inhibitor, if the timing of the last dose is known, designed to ensure patients have therapeutic anti-fXa activity levels. If the timing of the last dose of FXa inhibitor is unknown, the and exanet bolus must begin as soon as possible—following the signing of the ICF and completion of pre-treatment procedures—but no later than 3 hours following the signing of the ICF.

Patients will receive one of two dosing regimens of and exanet based on which FXa inhibitor they received (see Section 6.2) and the dose and timing of the most recent dose. For anti-fXa activity and diagnostic evaluations to support hemostatic efficacy (e.g., imaging tests, hemoglobin levels), baseline is defined as the most recent assessment prior to the start of the and exanet bolus. For post-baseline assessments, time 0 is defined as the end of the continuous and exanet infusion. Adverse Events and survival will be followed through the Day 30 post-treatment visit.

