Specifically for ICH, the primary efficacy outcome is based on reducing/preventing the increase in volume and/or thickness of the hemorrhage, as judged by CT/MRI. An excellent hemostatic outcome requires an effect by the 1-hour post-infusion time point that is maintained through the 12-hour time point. Importantly, the time period between the baseline CT/MRI and start of andexanet dosing should be minimized. Otherwise, significant hemorrhage expansion occurring early after baseline imaging counts against hemostatic efficacy even if prior to andexanet administration.

There are currently no clinical endpoints established or validated to evaluate hemostatic efficacy for ICH. Such a clinical endpoint would be extremely difficult to standardize across the different intracranial compartments of bleeding (e.g., intracerebral [intraparenchymal and intraventricular, subarachnoid, subdural) since the clinical presentations and severity of deficits would vary greatly amongst these compartments. Intraventricular hemorrhage expansion generally impacts level of consciousness but may have little impact on focal stroke deficits (NIHSS) (Appendix H) given their midline location. Subdural and subarachnoid hemorrhage expansion would have to be quite large to produce sufficient mass effect to result in focal neurologic symptoms. Amongst intracerebral parenchymal hemorrhages, there is great variability in brain eloquence (specific brain regions that directly control function) which dramatically varies the clinical effects of hemorrhage expansion (i.e., brainstem being much more eloquent than cortex). CT/MRI-based volumetric measurement is thus the most direct way to evaluate hemostatic efficacy. A clinical endpoint for ICH such as neurologic deterioration (defined as National Institutes of Health Stroke Scale [NIHSS] (Appendix H) worsening of 4 or more points or Glasgow Coma Scale [GCS] worsening of 2 or more points) is a more indirect measure of hemostatic efficacy since it is impacted by several factors not related to hemostasis, such as initial hematoma volume, edema, infection, and other medical complications [26]. That said, the best clinical measure of focal neurologic change is captured by the NIHSS (Appendix H) and the best clinical measure of change in consciousness would be captured by the GCS. Modified Rankin scores (mRS) are used to evaluate disability at 3 months and are designed to capture longer term changes in status. The NIHSS (Appendix H), GCS, and mRS

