11.5.4. Exploratory Efficacy Endpoints

The following additional efficacy endpoints will be analyzed as exploratory:

- The number of patients receiving one or more red blood cell transfusions from the start of the andexanet bolus through 12 hours after the end of andexanet infusion.
- For patients receiving apixaban, rivaroxaban, or edoxaban, to evaluate the decrease in free fraction of the FXa inhibitor following and examet administration.
- The number of red blood cell units transfused per patient from the start of the andexanet bolus through 12 hours after the end of the andexanet infusion.
- The use of non-study-prescribed blood products and/or hemostatic agents.
- The occurrence of re-bleeding following and examet treatment. Re-bleeding is defined as follows: recurrent bleeding from the same or another anatomical site, or new bleeding from a different anatomical site within 24 hours of initial and examet treatment and after achieving initial good/excellent hemostasis.
- Andexanet reversal of anticoagulant effect as measured through TG parameters (with, Endogenous Thrombin Potential [ETP] as the primary measure), for both the Tissue Factor (TF)-initiated assay and the non-TF-initiated assay.
- TFPI levels, both free and total, pre- and post-administration of andexanet.
- ATIII levels, pre- and post-administration of andexanet.
- Anti-factor IIa levels, pre- and post-administration of andexanet (enoxaparin patients only).
- The achievement of hemostatic efficacy in ICH patients at high risk of hematoma expansion.
- Change from baseline in GCS at 1 hour, 12 hours, and 30 days (for ICH patients only).
- Change from baseline in mRS at 1 hour, 12 hours, and 30 days (for ICH patients only).
- Change from baseline in NIHSS at 1 hour, 12 hours, and 30 days (for ICH patients only).

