5.5.2. Hemostatic Efficacy

For primary efficacy analysis, missing values (i.e., rated as Non-Evaluable due to administrative reasons) will be excluded from analysis. On the other hand, missing values due to non-administrative reason will be considered as treatment failure.

Non-evaluable for administrative reason is defined in the EAC Charter. The final decision regarding whether a patient is non-evaluable due to administrative or non-administrative reasons will be made by the EAC.

A sensitivity analysis will be performed with all patients rated as Non Evaluable classified as not reaching hemostatic efficacy.

5.5.3. **NIHSS**

Analysis will be performed only for the baseline and 12 hours post treatment. If the baseline or the 12-hour post-treatment NIHSS score is missing, the patient will be excluded from analysis.

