5.5.4. Ambiguous Values

In the case where a variable is recorded as "> x", " \geq x", " \leq x", " \leq x", then for analysis purposes a value of x will be taken. Where a range of values is quoted the midpoint of the range

will be taken. In the case where a patient records more than one score for any particular measure, the worst of the recorded scores will be taken for analysis purposes. In all cases, sites will be queried first to determine whether a more precise value is available.

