5.9. Data Derivation

- The following derivation rules will apply: unless missing data is imputed using the
 imputation methods described above, all tabulations involving change from baseline data
 will only include subjects with cohort data i.e. with data at baseline and at follow-up.
 Change from baseline will be calculated as follow-up values minus baseline value.
 Percentage changes from baseline will be rounded to 1 decimal place.
- For analysis purposes, 1 month = 30 days and duration in months will be rounded to 1 decimal place.
- Any derived data recorded in hours will be rounded to 1 decimal place.
- All calculation of length of time, including age, should be performed using SAS function to account for leap year.
- Height in inches will be converted to centimeters by multiplying by 2.54 and rounding to the nearest integer.
- Weight in lbs will be converted to kg by dividing by 2.2046 and rounding to 1 decimal place.
- Body mass index (BMI) will be calculated as weight (kg) / (height (cm)/100)² rounded to 1 decimal place.
- Temperature in Fahrenheit will be converted to Celsius by subtracting 32 and dividing by 1.8.

- Hemoglobin in g/L will be converted to mmol/L by multiplying by 0.06206 and rounding to 2 decimal places.
- To convert from g/dL to g/L multiply by 10.
- To convert from mg/dL to g/L multiply by 0.01 and round to 2 decimal places.
- To convert from mEq/L to mmol/L multiply by 1.
- To convert from µkat/L to U/L multiply by 1.
- For white blood cell and platelet count then $10^9/L = 10^3/\text{mm}^3$.
- For each white blood cell differential (Neutrophils, Lymphocytes, Monocytes, Eosinophils, Basophils) to convert from % to 10⁹/L by multiplying the value by the WBC (10⁹/L) and dividing by 100 and rounding to 1 decimal place.
- For creatinine to convert from μmol/L to mg/dL divide by 88.4173 and round to 1 decimal place.
- For serum glucose to convert from mmol/L to mg/dL divide by 0.0555 and round to 1 decimal place.
- For blood urea nitrogen to convert from mmol/L to mg/dL divide by 0.3651 and round to 1 decimal place.
- For total and direct bilirubin to convert from μmol/L to mg/dL to μmol/L divide by 17.0999 and round to 1 decimal place.
- For calcium to convert from mmol/L to mg/dL divide by 0.2495 and round to 2 decimal places.
- For phosphorous to convert from mmol/L to mg/dL divide by 0.3229 and round to 2 decimal places.
- For plasma concentrations that are lower than lower level of quantification (LLOQ) then

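### GCS and NIHSS change is summarised only in ICH patients with a follow-up score, so deaths leave analyses meant to detect worsening; SAP 5.5.3 also contradicts the planned NIHSS visits

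*SAP*

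**What the plan says.** **Aim and summaries.** SAP 5.15.1.10 covers mRS, GCS and NIHSS together and states: "The primary goal of these scale analyses is to detect any clinical worsening in ICH patients". GCS and NIHSS are summarised as raw score and change from baseline (mean, SD, median, CI). mRS is summarised as the proportion scoring 0 to 2 at each visit.

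**Who is included.** Under SAP 5.9, unless a value is imputed, change-from-baseline tables "will only include subjects with cohort data i.e. with data at baseline and at follow-up". SAP 5.5 contains no imputation rule for GCS or NIHSS. For NIHSS, SAP 5.5.3 adds: "If the baseline or the 12-hour post-treatment NIHSS score is missing, the patient will be excluded from analysis". It makes no exception for death.

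**NIHSS visits.** SAP 5.5.3 says: "Analysis will be performed only for the baseline and 12 hours post treatment". SAP 5.15.1.10 lists baseline, 1 hour, 12 hours and Day 30, and says that all efficacy-population patients with ICH are included. Protocol 11.5.4 lists "Change from baseline in NIHSS at 1 hour, 12 hours, and 30 days (for ICH patients only" among the exploratory endpoints.

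**More than one score.** Under SAP 5.5.4, if a patient has several scores for a measure, "the worst of the recorded scores will be taken for analysis purposes", after the site has been queried. Protocol 3.1 says that "baseline is defined as the most recent assessment prior to the start of the" bolus, in a sentence about anti-fXa activity and diagnostic evaluations supporting hemostatic efficacy.

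**The concern.** An analysis meant to find deterioration should not lose the patients who deteriorated most. Neither scale has a value for death: GCS runs from 3 to 15 (SAP 4.5.6) and NIHSS from 0 to 42 (SAP 4.5.8). With no death rule and tables limited to patients with both scores, a patient who dies before a visit is absent from that visit's change summary. A stable or improved mean change at Day 30 would then describe survivors with a score, not the ICH patients who were treated. Protocol 3.4.2 describes the prognosis of ICH as markedly poor, so the loss cannot be assumed to be negligible.

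The NIHSS conflict is a separate defect. A programmer who follows 5.5.3 produces one post-baseline time point. One who follows 5.15.1.10 produces three. Following 5.5.3 leaves two of the protocol's three NIHSS time points without an analysis.

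**Working it through.** The plan states no figure for these analyses, so there is none to reproduce. The check compares the rules and then illustrates their effect.

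**1. What happens to a death, by rule**

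| Analysis | Rule | Patient who dies before the visit |
|---|---|---|
| GCS change | SAP 5.9; no imputation | Leaves that visit's summary |
| NIHSS change, if 5.5.3 governs | Baseline and 12 h only; excluded if either is missing | Lost if death precedes the 12 h score; Day 30 not analysed |
| NIHSS change, if 5.15.1.10 governs | SAP 5.9 at 1 h, 12 h and Day 30 | Leaves that visit's summary |
| mRS 0-2 | 6 = dead (SAP 4.5.7) | Counted as above 2, if the 6 is recorded |
| Hemostatic efficacy | SAP 5.5.2: non-administrative missing = failure; Protocol 11.1 gives death as an example of a clinical reason | Counted as failure |
| 30-day mortality | SAP 5.16.3, by bleeding type, exact 95% CI | Counted |

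The SAP therefore already counts such cases as failures for hemostasis, but has no equivalent rule for GCS and NIHSS change.

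**2. Whether the mRS fills the gap.** It does so only in part. A patient with mRS 4 at baseline who dies is above 2 at both times and so shows no worsening on the split.

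**3. Size for a worsening proportion (inputs assumed).** The documents give neither ICH mortality *m* nor the share of survivors who worsen *w*. Among survivors the proportion is *w*. Counting deaths, it is (1 - m)w + m. The difference is m(1 - w).

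- m = 0.10, w = 0.20: 0.10 × 0.80 = 8.0 points
- m = 0.15, w = 0.15: 0.15 × 0.85 = 12.75 points
- m = 0.20, w = 0.10: 0.20 × 0.90 = 18.0 points

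In counts, take the protocol's minimum of 110 evaluable ICH patients with 10% mortality (11 deaths, 99 survivors) and 10 survivors worsening. The survivor figure is 10/99 = 10.1%. With deaths it is 21/110 = 19.1%.

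**4. Direction for a mean change (inputs assumed).** Let N = 110, with a survivor mean change of +0.5 on GCS and -2 on NIHSS. Let baseline in those who die be GCS 12-14 and NIHSS 10-15. Score each death at the worst value (3 or 42). The full mean is [S × survivor mean + D × (worst - baseline)]/N, with S survivors and D deaths.

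| Mortality (D) | GCS mean change | NIHSS mean change |
|---|---|---|
| Survivors only | +0.5 | -2 |
| 5% (6) | -0.02 to -0.13 | -0.42 to -0.15 |
| 10% (11) | -0.45 to -0.65 | +0.90 to +1.40 |
| 20% (22) | -1.40 to -1.80 | +3.8 to +4.8 |

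For example, GCS at 10% mortality and baseline 12 gives (99 × 0.5 - 11 × 9)/110 = -0.45. The table shows direction only, because the results depend on an arbitrary score for death.

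**5. Worst-score rule at baseline.** With two readings and independent normal error of SD *s*, the worse one is expected to lie s/√π beyond the mean: 0.28, 0.56 or 1.13 points for s = 0.5, 1 or 2. At follow-up this is conservative. At baseline it shifts change toward improvement by the same amount. Appendix A of the protocol schedules one baseline GCS and one baseline NIHSS, so duplicates should be few.

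**The case against.** The strongest reply is that the deaths are in plain sight. The stated aim covers three scales, one of which has a death category. ICH mortality has its own figure, and hemostatic efficacy counts non-administrative missing outcomes as failures. Survivor change beside these is an ordinary display for exploratory endpoints. This stands against any inference that the plan conceals deaths. It does not repair the GCS and NIHSS change summaries, and the mRS split misses patients already above 2 at baseline.

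Four stronger readings are tempting but not supported:

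- *Mean change must improve as mortality rises.* This is not mechanical. It needs those who died to have been heading for worse change than survivors, which is plausible but not shown.
- *The planned result is biased by 8 to 18 points.* The SAP plans no proportion worsened for GCS or NIHSS, and both inputs are assumed.
- *SAP 5.5.4 contradicts the protocol's baseline rule.* That rule gives imaging and hemoglobin as its examples. Protocol 3.1 lists the neurologic scales among the hemostatic assessments, so its reach is arguable, but it is not expressly stated for them.
- *The SAP ignores a protocol deterioration endpoint.* Protocol 3.4.3 mentions an NIHSS "worsening of 4 or more points or Glasgow Coma Scale [GCS] worsening of 2 or more points" only as an example, and explains that it is a more indirect measure of hemostasis. The listed endpoints are changes from baseline.

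Timing also counts. SAP 1.0 refers to 477 locked patients, and SAP 3.5 says descriptive submissions have been made. A table added now is a later analysis and must say so.

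**Conclusion.** The point holds in two parts. First, the GCS and NIHSS change summaries leave out patients who die before the visit, which does not fit the stated aim of detecting worsening. This follows from SAP 5.9 and 5.5.3 and the absence of any death value; the SAP does not say it outright. Second, SAP 5.5.3 contradicts SAP 5.15.1.10 and Protocol 11.5.4 on NIHSS visits, and its exclusion sentence conflicts with the inclusion of all ICH efficacy patients.

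The size cannot be obtained from the documents. The 8 to 18 points is illustrative, applies to Day 30 only, and rests on assumed mortality and survivor worsening of 10-20% each. The baseline side of the worst-score rule is minor. These endpoints are exploratory and no primary conclusion changes, but the correction is worth making because it is cheap and uses data already collected.

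**What to change.** 1. **SAP 5.5.3:** replace both sentences. Analyse NIHSS at 1 hour, 12 hours and Day 30, and apply exclusions per visit. Removing only the 12-hour restriction would leave the next sentence excluding anyone who dies before the 12-hour score.
2. **SAP 5.15.1.10:** add a supportive table, dated and labelled as added after the data lock. At each visit give the proportion with deterioration: NIHSS up by 4 or more, GCS down by 2 or more (the example thresholds in Protocol 3.4.3), or death by that visit. Give exact 95% CIs and the number missing for reasons other than death. State how an untestable GCS item is handled, since SAP 4.5.6 gives no rule for the total.
3. **Existing change tables:** keep mean and median change, labelled as survivors with a score at that visit.
4. **SAP 5.5.4 (minor):** state that the worst-score rule applies after baseline only, and that baseline for these scales is the last score before the bolus.

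The cost is some SAP wording and one extra table, with no new data collection. Any deterioration figure that counts deaths will look less favourable than one in survivors alone.

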4.5.7. Modified Rankin Score (mRS)

The mRS will be evaluated only for ICH patients. Ideally the initial assessment would be made in the pre-morbid state, which is not possible within the context of this study. Therefore, the assessment will be performed at baseline, at 1 hour, 12 post the end of andexanet infusion and at Day 30 follow-up. The scale runs from 0 to 6, running from perfect health without symptoms (0) to death (6).

- 0 No symptoms at all.
- 1 No significant disability. Able to carry out all usual duties and activities, despite some symptoms.

- 2 Slight disability. Able to look after own affairs without assistance, but unable to carry out all previous activities.
- 3 Moderate disability. Requiring some help, but able to walk without assistance.
- 4 Moderately severe disability. Unable to attend to own bodily needs without assistance, and unable to walk unassisted.
- 5 Severe disability. Requires constant nursing care and attention, bedridden, incontinent.
- 6 Dead.

mRS will be further defined at each time point as follows:

- 1 = for patients with of zero to 2, inclusive, and
- 0 = for patients with score greater than 2.

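### The SAP summarises mRS only as an unpaired proportion scoring 0–2 at each visit, so the protocol's exploratory change-from-baseline mRS endpoint has no analysis and worsening from a baseline of 3 or more cannot register in it

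*SAP*

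**What the plan says.** Protocol 11.5.4, like the synopsis, lists as an exploratory endpoint "Change from baseline in mRS at 1 hour, 12 hours, and 30 days (for ICH patients only".

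SAP 5.15.1.10 covers mRS, GCS and NIHSS together and states: "The primary goal of these scale analyses is to detect any clinical worsening in ICH patients". For mRS it counts "the number of patients with score of zero to 2, inclusive (i.e., qualified as success" and treats every higher score as failure. The statistic is a one-sample proportion with an exact 95% CI, shown separately at baseline, 1 hour, 12 hours and Day 30.

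SAP 4.5.7 describes the scale as "running from perfect health without symptoms (0) to death (6" and gives the same binary coding, with "0 = for patients with score greater than 2". Scores 3, 4, 5 and 6 therefore share one category. It also says of the baseline: "Ideally the initial assessment would be made in the pre-morbid state, which is not possible within the context of this study".

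The other two scales are handled differently in the same section. For GCS, "The sum of the three domains score will be summarized as the raw value and change from baseline"; NIHSS is likewise analysed both raw and as change.

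**The concern.** The endpoint in the protocol is a within-patient change. The planned statistic is a set of cross-sectional proportions, with no change score, shift table or paired comparison.

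This has two consequences for the mRS summary:

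- A patient who starts at 3 or more can deteriorate, or die, and stay in the same category throughout.
- Where the cut is crossed, only the net number of crossings shows. One patient getting worse and another getting better leave the proportion unchanged.

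A flat or rising 0–2 proportion from baseline to Day 30 is therefore compatible with real worsening, in a section whose stated aim is to find worsening. The SAP's list of main changes (5.17.2) does not mention or explain the different handling of mRS.

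**Working it through.** The documents give no sample size, power or expected rate for this analysis, so there is no planned figure to reproduce. The check is an enumeration.

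**Inputs.** Scale 0 to 6 with 6 = dead (SAP 4.5.7; Protocol Appendix D). Coding 1 if mRS is 0–2 and 0 if above 2 (SAP 4.5.7 and 5.15.1.10).

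**All possible worsening steps.** From a baseline of 0, 1, 2, 3, 4 or 5 to any higher score: 6 + 5 + 4 + 3 + 2 + 1 = 21.

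| Worsening step | Count | Changes the 0–2 coding? |
|---|---|---|
| From 0, 1 or 2 to 3, 4, 5 or 6 | 3 × 4 = 12 | Yes |
| Within 0–2 (0→1, 0→2, 1→2) | 3 | No |
| From 3, 4 or 5 upward (3→4, 3→5, 3→6, 4→5, 4→6, 5→6) | 3 + 2 + 1 = 6 | No |

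Registered: 12. Missed: 3 + 6 = 9. From a baseline of 3 or more, 0 of 6 register, and the missed steps include all three to death (3→6, 4→6, 5→6). This counts kinds of step, not patients; the documents give no frequencies.

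**Cancellation.** If one patient goes 2→4 and another 3→2, the count at 0–2 changes by −1 + 1 = 0, although one patient worsened.

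**Illustration, on assumed rates.** Take the protocol's minimum of about 110 evaluable ICH patients. Assume 60% start at mRS 3 or more (0.60 × 110 = 66), 40% of those worsen or die (0.40 × 66 ≈ 26), and nobody else changes.

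- SAP summary: (110 − 66)/110 = 44/110 = 40.0% at baseline, and 44/110 = 40.0% at Day 30.
- Change from baseline: 26/110 = 23.6% worsened.

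Keeping 40% worsening and varying the assumed share at 3 or more:

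- 40% share: 44 patients, 18 worsen, 18/110 = 16.4% missed.
- 80% share: 88 patients, 35 worsen, 35/110 = 31.8% missed.

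These figures show the mechanism and are not estimates. The six steps from 3 or more are missed whatever the share.

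**Do the other scales cover the gap?** GCS totals run from 3 to 15 (SAP 4.5.6) and NIHSS from 0 to 42 (SAP 4.5.8); neither has a value for death. Unless a value is imputed, change tables include only patients with data at both times (SAP 5.9), and SAP 5.5 has no imputation rule for GCS. SAP 5.5.3 restricts NIHSS analysis to baseline and 12 hours and drops patients with a missing score, although 5.15.1.10 also lists 1 hour and Day 30. A patient who dies before Day 30 therefore has no planned Day 30 change on either scale.

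**The case against.** The case for leaving the plan alone has substance.

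- **Deaths are reported elsewhere.** A reader might infer that deaths in ICH patients would be hidden. The documents do not support that: SAP 5.16.3 gives 30-day mortality with exact 95% CIs by bleeding type, and summarises cause of death. That analysis uses the safety population and is not broken down by baseline mRS, so it does not replace the mRS endpoint.
- **The stated aim belongs to three scales.** A reader might infer that the trial cannot detect neurological worsening. It can, in part: GCS and NIHSS get change from baseline. Protocol 3.4.3 treats NIHSS and GCS as the best clinical measures of focal change and of consciousness, defines deterioration by those two, and describes mRS as a longer-term disability measure. This stands for survivors, within the limits on NIHSS timing and on scoring death shown above.
- **Baseline severity is unknown.** It is tempting to say that most ICH patients start above 2, since baseline is scored during the bleed. The documents give no share. They exclude GCS below 7 and intracerebral hematoma above 60 cc (Protocol 4.2), and mRS 3 means walking without help. No percentage can be attached to the loss.
- **The acute baseline is imperfect.** A one-level change at 1 or 12 hours is hard to interpret. That calls for caution in reading change, but change is the protocol's own endpoint.
- **The protocol leaves detail to the SAP, and the endpoint is exploratory.** Both are true. Adding a 0–2 summary is within that latitude; leaving the named endpoint without any analysis is not. The wording in SAP 4.5.7 may imply that raw scores are kept, but no follow-up analysis of raw or change scores is specified; SAP 5.11.1 covers mRS only as a baseline characteristic.

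**Conclusion.** The mismatch is real and limited. An exploratory endpoint named in the protocol has no matching analysis in the SAP. The substitute cannot register 9 of 21 possible worsening steps, including every step from a baseline of 3, 4 or 5, and it lets opposite crossings cancel. This follows from the coding alone and needs no assumption about baseline severity; only the 110-patient illustration does.

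The consequence is confined to the mRS summary in ICH patients. Neither primary endpoint is affected, and the gap in worsening is partly covered by the mortality analysis and by GCS and 12-hour NIHSS change. It still warrants correction: mRS is the only one of the three scales that can place death and disability on one within-patient measure at Day 30, and the planned coding discards that for anyone starting at 3 or more.

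**What to change.** In SAP 5.15.1.10 and Table 14.2.4.8a, add for ICH patients at 1 hour, 12 hours and Day 30:

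1. a shift table of baseline mRS by mRS at that visit, levels 0 to 6;
2. the proportion worsening by at least one level from the patient's own baseline, with an exact 95% CI.

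State that a patient who has died by the visit is scored 6. Keep the 0–2 proportions as a supplement. Record the addition in SAP 5.17.2 as restoring the protocol endpoint. Because the SAP's table list is labelled as samples that will not be updated, put the requirement in the text of 5.15.1.10 and not only in a table title.

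The cost is a few sentences and one more table, from assessments already scheduled in Protocol Appendix A. The small downside is that changes at 1 and 12 hours need a cautionary note, since the SAP itself regards the acute baseline as less than ideal.
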